12. EVALUATION AND CALCULATION OF VARIABLES BY ASTRAZENECA

12.1 Calculation or derivation of safety variable(s)

12.1.1 Other significant adverse events

During the evaluation of the AE data, AstraZeneca medically qualified experts will review the list of AEs that were not reported as SAEs and AEs leading to withdrawal. Medically qualified experts on the study team will also review the safety data to select significant AEs of particular clinical importance/special interest, which will be considered OAEs/events of special interest and reported as such in the Clinical Study Report.

Examples of these are marked haematological and other laboratory abnormalities, and certain events that lead to intervention (other than those already classified as serious), dose reduction or significant additional treatment.

12.2 Calculation or derivation of demographic and efficacy variables

12.2.1 Calculation and derivation of Charlson Comorbidity Scale

The calculation of the Charlson Comorbidity Scale score will be done electronically; investigators will only need to confirm that the patient has any of the co-morbid conditions by term.

12.2.2 Calculation and derivation of PRO variables

The SF-36v2 Acute scoring will be used (SF-36 health survey manual and interpretation guide, [Ware et al, 2000](#)). Two overall summary scores, the physical component summary score and the mental health component summary score, will be derived as the principal

method of reporting SF-36v2 Acute results. Each domain score will also be derived individually.

The Day 29 value will be taken as the initial value, and the Day 90 value will be taken as the follow-up value.

12.2.3 Calculation and derivation of Acute Physiology and Chronic Health Evaluation (APACHE) II Score

The calculation of the APACHE II score will be done electronically; investigators will only need to enter the values of the parameters measured into the eCRF.

12.2.4 Calculation and derivation of Glasgow Coma Score

The calculation of the Glasgow Coma Score will be done electronically; investigators will only need to answer the individual questions in the eCRF.

For each of the categories of eye, verbal and motor response, a point score is assigned to the level of response. The Glasgow Coma Score is the sum of these three scores. For further details, see [Appendix F](#).

12.2.5 Calculation and derivation of the modified Sequential Organ Failure Assessment (SOFA) Scores

A point score is given to each of the variables recorded for the 5 categories of respiration, coagulation, liver, cardiovascular, and renal. The total modified SOFA score is calculated from the sum of these individual scores. A modified SOFA score will be calculated (five categories: respiration, coagulation, liver, cardiovascular, and renal) for all timepoints in [Table 1](#). The calculation of the modified SOFA score will be done electronically; investigators will only need to enter the values of the parameters measured into the eCRF.

The worst BP and saturation values of the day should be used, and if a drug holiday or no value is collected, the last assessment performed should be the value for that day.

For further details of the modified SOFA Score, see [Appendix G](#).

12.2.6 Calculation and derivation of ventilator use and pulmonary assessment parameters

The predicted body weight will be calculated using the height at screening. The value for males is calculated by:

$$50 + 0.91 \times (\text{centimetres of height} - 152.4).$$

The predicted body weight for females is calculated by:

$$45.5 + 0.91 \times (\text{centimetres of height} - 152.4).$$

Ventilator-free days

VFD at Day 29 (over 28) days is defined as:

- The number of days after starting unassisted breathing up to and including Day 29, assuming a patient survives for at least 2 consecutive calendar days after starting unassisted breathing and remains free of assisted breathing
 - If a patient returns to assisted breathing and subsequently achieves unassisted breathing prior to Day 29, VFD will be counted from the end of the last period of assisted breathing up to and including Day 29 (unless the period of assisted breathing was less than 24 hours and the purpose of the assisted breathing was a surgical procedure).
 - If a patient was receiving assisted breathing at Day 29 or dies prior to Day 29, VFD will be zero.
 - If a patient never requires assisted breathing, the VFD will be 28 days.
- The 28-day study period is from Day 2 to the Day 29+2 telephone contact.

Unassisted breathing is defined as:

- Extubated with face mask, nasal prong oxygen or room air, OR
- T-tube breathing, OR
- Tracheostomy mask or collar, OR
- Continuous positive airway pressure less than or equal to 5 cm water without pressure support or intermittent mandatory ventilation assistance.

Investigators will not be required to calculate VFDs; VFDs will be derived. VFDs at Day 15 (over 14 days) will be derived in a similar manner to above.

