5.1 Inclusion criteria

For inclusion in the study patients must fulfil the following criteria.

1. Patients undergoing a first episode of sepsis during this hospitalisation (including transfer from another hospital).
2. Objective clinical evidence of infection; at least 1 of the following (see also inclusion criterion 5). Including:
 - Perforated viscus.
 - WBC and/or pathogens in a normally sterile body fluid.
 - Radiographic evidence of pneumonia.
 - Signs of a local source of infection such as cellulitis.
 - A syndrome associated with a high risk of infection (eg, ascending cholangitis).
 - Positive culture from blood or from another normally sterile body fluid prior to study drug administration.
 - Evidence of an infecting organism such as pneumococcal antigen or Legionella antigen.
3. Patients must meet at least 2 of the following 4 SIRS criteria at least one of which must be the core temperature criterion or the WBC criterion (see also inclusion criterion 5); these criteria do not have to be met simultaneously; the actual values and the date and time that the criteria were met will be collected.
 - Hypothermia by core temperature $<36^{\circ}\text{C}$, or hyperthermia $>38^{\circ}\text{C}$ measured via any means.
 - Heart rate (HR) >90 beats per minute.
 - Respiratory rate (RR) >20 breaths/minute related to septic event or partial pressure of arterial carbon dioxide (PaCO₂) <32 mmHg related to septic event or requiring mechanical ventilation related to septic event.
 - Total WBC absolute count >12000 cells/mm³ or <4000 cells/mm³. In the presence of granulocyte-stimulating factor, for those patients whose WBC absolute count is >12000 cells/mm³, they must have a fever and at least one other criterion (RR or HR).
4. Patients must meet criteria for cardiovascular and/or respiratory dysfunction (see also inclusion criterion 5). Newly developed organ failures must be due to the acute

THIS IS A PRINTED COPY OF AN ELECTRONIC DOCUMENT. PLEASE CHECK ITS VALIDITY BEFORE USE.

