7.6.4 Ventilator use and pulmonary assessment

Whether a patient requires mechanical ventilation will be recorded at the timepoints specified in [Table 1](#). If a patient requires mechanical ventilation, data will be recorded regarding whether ventilator weaning was attempted (see [Appendix H](#) for recommended procedures for ventilator weaning). The definitions of VFDs and unassisted breathing are provided in [Section 12.2.6](#).

For patients on mechanical ventilation the following ventilator settings will be recorded daily at the timepoints specified in [Table 1](#): tidal volume, FiO₂, peak airway pressure over the last 24 hours, plateau pressure, positive end expiratory pressure, and RR. For patients on mechanical ventilation an arterial blood gas (pH, PaO₂, PaCO₂ and FiO₂ at the time the sample was obtained), if available, will be recorded once per day. If more than one value is obtained, the value closest to 08:00 will be used.

Predicted body weight will be recorded on the ventilator eCRF for assessment of tidal volume.

Ventilator-free days

The number of VFDs will be derived. This is a composite endpoint including days free of mechanical ventilation and mortality.

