13.3.4 Ventilator-free days

Summary statistics (mean, median, standard deviation [SD], minimum, and maximum) of VFDs over 28 days will be presented by treatment group. Missing data will be handled using a last observation carried forward (LOCF) approach when calculating VFDs for each patient. A histogram of VFD will also be produced for each treatment group.

For the formal statistical analysis, an analysis of covariance model will be fitted for VFDs allowing for treatment group and the following baseline covariates:

APACHE II score (four categories based on the quartiles of the baseline score), age (two categories: <60 and 60 or older), region (three categories: Australia, North America [Canada & USA] and All Other) and an indicator variable if the patient was on mechanical ventilation at baseline (two categories: yes or no).

The difference in VFDs for each of the comparisons: AZD9773 dose 1 versus placebo, AZD9773 dose 2 versus placebo, AZD9773 dose 1 and 2 versus placebo will be presented in terms of the difference in the Least Square Means (LSMeans) and the associated two-sided 80% CI and one-sided p-value. Additionally, a two-sided 95% CI and two-sided p-value will also be presented.

For the PP population, the effect of other baseline variables (examples include baseline TNF, Xigris use prior to study treatment and presence of shock at baseline) on the treatment comparisons will also be explored via a series of analyses including the covariates as specified above for each of the levels of these baseline variables separately. The difference in the treatment LSMean and the associated two-sided 80% CI from these analyses (along with the results from the baseline covariates fitted in the statistical analysis above) will be presented graphically on the same plot. Additionally, an analysis of variance will also be performed for the PP and ITT populations (with no covariates and only treatment as a factor).

VFDs at Day 15 (over 14 days) will be analysed in a similar manner to above.

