13.3.6 Organ failure-free days, shock-free days, and ICU-free days

Organ failure-free days, shock-free days, and ICU-free days will be summarised and analysed in the same way as for VFD (see Section 13.3.4).

13.3.7 7-day mortality, 28-day mortality and mortality at Day 90

Seven-day mortality and 28-day mortality will be summarised by treatment group. The formal analysis will be undertaken for each the comparisons: AZD9773 dose 1 versus placebo, AZD9773 dose 2 versus placebo, AZD9773 dose 1 and 2 versus placebo separately using a Cochran-Mantel-Haenszel test in which the test will be stratified using the same covariates as for VFD. The corresponding relative risk, two-sided 80% CI and one-sided p-value will be calculated using the procedure PROC FREQ in SAS. Additionally, a two-sided 95% CI and two-sided p-value will also be presented.

An unstratified analysis will also be performed for the PP and ITT populations. Additionally, for the PP population, the impact of other baseline variables (examples include baseline TNF, Xigris use prior to study treatment and presence of shock at baseline) on the treatment comparisons will be explored by undertaking a series of analyses for each of the levels of these baseline variables separately, and the relative risks along with the associated two-sided 80% CIs from these analyses will be presented graphically.

In the event that the 7-day mortality and 28-day mortality status is unknown for some patients, they will be excluded from the PP population. However, for the ITT population they will be included as though they had died. Further sensitivity analyses may be undertaken depending on the number of such patients.

A Kaplan-Meier curve of time to death will also be produced and both a stratified (using the same covariates as for the analysis of 7 and 28-day mortality) and unstratified log rank test will be undertaken. If the 7-day or 28-day mortality status is unknown for some patients, they will be censored at the last known date the patient was alive.

Mortality at Day 90 will be considered in the same way as 7-day and 28-day mortality.

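### Section 12.2.6 gives a never-ventilated patient who dies before Day 29 both 28 and 0 ventilator-free days; in ITT only, LOCF can also give ventilator-free days to patients the mortality analysis counts as dead

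*Protocol*

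**What the plan says.** **Scoring.** Section 12.2.6 counts days from the start of unassisted breathing through Day 29, provided the patient then survives two consecutive calendar days and stays off assistance. Under that definition it lists special cases side by side. One reads "If a patient was receiving assisted breathing at Day 29 or dies prior to Day 29, VFD will be zero". The next reads "If a patient never requires assisted breathing, the VFD will be 28 days". Neither refers to the other, and the second has no survival condition. The 14-day VFDs are to be derived in a similar way.

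**Who can be unventilated.** Section 5.1 states "Patients must meet criteria for cardiovascular and/or respiratory dysfunction", and Table 2 defines the cardiovascular criterion through hypotension and vasopressors, not ventilation. The primary model in section 13.3.4 includes "an indicator variable if the patient was on mechanical ventilation at baseline", with levels yes and no.

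**Nature of the endpoint.** Section 7.6.4 says of VFDs: "This is a composite endpoint including days free of mechanical ventilation and mortality".

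**Missing data.** Section 13.3.4: "Missing data will be handled using a last observation carried forward (LOCF) approach when calculating VFDs for each patient". Vital status is not mentioned. Section 13.3.7, on mortality, says "In the event that the 7-day mortality and 28-day mortality status is unknown for some patients, they will be excluded from the PP population", and then "However, for the ITT population they will be included as though they had died". In the Kaplan-Meier analysis the same patients are censored when last known alive. Section 13.1 names the PP population for all efficacy data and adds an ITT analysis of the formally tested endpoints, VFDs among them.

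**The concern.** A definition that is applied by derivation, as section 12.2.6 says this one is, has to return a single value for every patient. Here a foreseeable patient gets the best and the worst score at once, and the order of the derivation steps could decide which one enters the analysis. The choice matters in substance. If 28 is used, a never-ventilated patient scores the same alive or dead, so for that subgroup the endpoint stops being a composite with mortality.

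Two smaller gaps adjoin it. The zero rule stops short of Day 29, while the count includes Day 29. And in ITT one patient can contribute ventilator-free days to the VFD analysis and a death to the mortality analysis, although section 12.2.6 would give a death zero.

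**Working it through.** **1. The plan's own figure.** Inputs from section 13.4: SD 11.380, 100 per group, difference 4.2, one-sided 10%, power 90%.

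- SE = 11.38 × √(2/100) = 1.609
- Power = Φ(4.2/1.609 − 1.2816) = 0.908
- Patients needed for 90%: 97 per group

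The sample-size statement reproduces and is not in dispute.

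**2. The rules applied to particular patients.**

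| Patient | Death rule | Never-ventilated rule |
|---|---|---|
| Never ventilated, alive after Day 29 | not met | 28 |
| Never ventilated, dies before Day 29 | 0 | 28 |
| Never ventilated, dies on Day 29 | not met | 28 |
| Off the ventilator for good on Day 10, dies on Day 29 | not met | not met; the count gives 29 − 10 = 19 |

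The second row is the contradiction. The last two are the boundary gap: by section 4.1, Day 1 is only the remainder of the calendar day of first dosing, so Day 29 is the last of the 28 full days.

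**3. Size of the 28-or-0 choice.** Let f be the never-ventilated share of an arm and m the proportion of those who die before Day 29. The protocol gives neither; both are assumptions. Change in arm mean = 28 × f × m:

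| | m = 10% | m = 20% | m = 30% |
|---|---|---|---|
| f = 10% | 0.28 | 0.56 | 0.84 |
| f = 20% | 0.56 | 1.12 | 1.68 |
| f = 30% | 0.84 | 1.68 | 2.52 |

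The between-arm difference changes only if f × m differs between arms. To illustrate, assume that the 28-day mortality reported for the earlier D-CytoFab study in section 2.4 (37% and 26%, a gap of 11 points in favour of active treatment) also held among never-ventilated patients, and keep the SD at 11.38. Loss of effect = 28 × f × 0.11:

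| f | Loss (days) | Effect left of 4.2 | Power |
|---|---|---|---|
| 10% | 0.31 | 3.89 | 0.872 |
| 20% | 0.62 | 3.58 | 0.828 |
| 30% | 0.92 | 3.28 | 0.775 |

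**4. Size of the LOCF mismatch (ITT only).** Let u be the share of an arm with unknown Day 29 status and last seen breathing unassisted, and v the VFDs that LOCF gives them; both are assumed. Difference in ITT arm mean between LOCF and zero = u × v. From u = 1%, v = 15 to u = 5%, v = 28 this runs from 0.01 × 15 = 0.15 to 0.05 × 28 = 1.40 days. A patient last seen on assisted breathing scores zero either way.

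**The case against.** The strongest reply is that the intent can be recovered. Section 7.6.4 calls VFDs a composite that includes mortality, the death rule carries no condition, and the main definition presupposes survival after coming off the ventilator. That stands: zero is the natural reading. It does not remove the overlap, because the 28 rule carries no condition either. Nor can this be left to the SAP as detail, since the protocol has already fixed both rules and a SAP would have to override one of them.

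Exclusion criterion 8 keeps out patients for whom life support is unlikely to be maintained, which should make deaths without ventilation less common. That bears on frequency, not on the contradiction.

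Two stronger readings are tempting.

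- *An imbalance in such deaths inflates the false-positive rate.* The documents do not support this. Either score would apply alike to all arms; with no treatment effect, never-ventilated deaths differ between arms only by chance, which the standard error covers. The illustrated harm is dilution and lost power.
- *The primary endpoint generally rewards loss to follow-up.* Section 13.3.7 removes patients of unknown 28-day status from PP, the population named first for efficacy. The mismatch is confined to ITT and to patients last seen breathing unassisted. Section 5.4.4 also keeps patients who stop study drug in follow-up for mortality, and section 13.3.7 allows further sensitivity analyses.

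**Conclusion.** The 28-or-0 overlap is an error in the primary endpoint as written. It affects PP and ITT alike and should be corrected before unblinding. The Day 29 boundary belongs in the same correction. The LOCF mismatch is real but lesser, for the reasons of scope given above; that LOCF keeps a patient alive is its effect, not something section 13.3.4 states.

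The size cannot be derived from the protocol. Under the assumed ranges, the scoring choice moves an arm mean by 0.28 to 2.52 days; under the added mortality assumption it takes power from 0.908 to between 0.872 and 0.775. The LOCF mismatch moves an ITT arm mean by 0.15 to 1.40 days. The contradiction does not depend on these figures.

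**What to change.** **Section 12.2.6.** State that death on or before Day 29 gives VFD = 0 whether or not the patient was ever ventilated, and that this takes precedence over every other rule. Restrict the score of 28 to never-ventilated patients alive at the end of Day 29. Keep all other conditions unchanged: the two consecutive calendar days of survival and unassisted breathing, counting from the last assisted period, and the exception for surgical assistance of less than 24 hours. Apply the same precedence to the 14-day VFDs.

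**Section 13.3.4.** For ITT patients whose vital status at Day 29 is unknown, set VFD = 0 to match the ITT mortality rule, and report LOCF for these patients as a sensitivity analysis. Keep LOCF for missing ventilator data in patients whose vital status is known.

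**Cost.** A few lines of text and no new data. The downside is a conservative score for the ITT patients of unknown status, expected to be few.

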4. STUDY PLAN AND PROCEDURES

4.1 Overall study design and flow chart

This Clinical Study Protocol has been subject to a peer review according to AstraZeneca standard procedures.

This is a randomised, double-blind, placebo-controlled, international multicentre Phase IIb study evaluating the efficacy and safety of multiple iv infusions of AZD9773 in patients with acute severe sepsis and/or septic shock (within 24 hours of organ failure).

The target population for the study comprises adult patients with severe sepsis and/or septic shock who have objective clinical evidence of infection, meet the criteria for systemic inflammatory response syndrome (SIRS), and have cardiovascular and/or respiratory failure according to the definitions in Section 5.1. Written informed consent for participation in the study is required from the patient (or his/her legally authorised representative) before any study-specific procedures are conducted.

Approximately 300 patients will be entered into the study (ie, allocated to study treatment) from approximately 100 centres. The maximum duration that a patient is expected to remain in the study including screening and the follow-up phone contact is approximately 91 days (about 13 weeks). An IDMC will be convened and will meet once 100 patients have reached Day 29 to review safety assessments and make recommendations to continue or stop the study based on safety findings (see Section 13.6).

The study design is presented in Figure 1 and the study plan is presented in Table 1. Day 1 is defined as time 0 hours (start of first infusion of study drug) to the end of that calendar day. The study comprises the following three periods:

Screening period

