 - ac Samples for multiplex assay for exploratory chemokines and for exploratory plasma renal panel should be taken at the same time as samples for cytokines or other blood samples and the date and time should be noted.
 - ad **28-day survival assessment must take place after a minimum 28 FULL CALENDAR days have elapsed since start of study and within 2 days after Day 29.**
 - ae HRQoL will be assessed via completion of the SF-36v2 Acute questionnaire by the patient or designate at Days 29 and 90.

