7.2.1 Follow-up procedures

The follow-up data will be collected and recorded in the appropriate sections of the eCRF (refer to Study Plan, Table 1). Whether a patient is alive or not at Day 29+2 and Day 90+14, should be recorded in the eCRF (see Table 1). Additionally, the question will be asked “Was aggressive medical care withdrawn?” for those patients who died. For patients discharged from a medical setting, a vendor specialising in home visitation and/or medical aftercare may assist in obtaining follow-up study information according to study procedures.

For HRQoL, the questionnaire may be completed face-to-face or by telephone. Completion of the questionnaire will be interviewer-led.

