Deterioration as compared to baseline in protocol-mandated laboratory values, vital signs and other safety variables should only be reported as AEs if they fulfil any of the SAE criteria or are the reason for discontinuation of treatment with the IP. However, the investigator may record such findings as an AE at his/her discretion in addition to completing an unscheduled laboratory/vital signs page with the information on the clinically significant test abnormality. If a deterioration in a laboratory value/vital sign is associated with clinical signs and symptoms, the sign/symptom will be reported as an AE and the associated laboratory result/vital sign will be considered as additional information. Any new or aggravated clinically relevant abnormal medical finding at a physical examination, dermal examination or lung auscultation as compared with the baseline assessment will be reported as an AE. Clinically relevant deterioration in

██████████
unscheduled assessments of laboratory/vital signs/ECG parameters should be reported on additional eCRF pages.

Wherever possible, the reporting investigator uses the clinical, rather than the laboratory term (eg, anaemia versus low haemoglobin value).

Overdose

Please refer to Section 1.2.

Pregnancy

Please refer to Section 1.3.

Deaths

All deaths occurring from provision of informed consent until Day 90 must be reported on the statement of death page. The cause of death may be reported as a SAE based on the criteria described in Section 7.3.2.

Follow-up of unresolved adverse events

After the initial AE/SAE report the investigator is required to follow up proactively each patient and provide further information to PAREXEL Clinical Studies Safety Centre on the patient's condition. During the study all AE/SAEs should be followed up to resolution or until the patient completes the study (ie, Day 90 or death) unless the event is considered by the investigator to be unlikely to resolve due to the patient's underlying disease (in these cases, the investigators must record their opinions in the patient's medical records), or the patient is lost to follow-up. Events still present at the time of death, and that were not the cause of death, should be classified as "ongoing". AstraZeneca and/or PAREXEL retain the right to ask for further information on any AE, which may be considered of interest.

Other significant adverse events

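### A patient who dies on Day 29 off the ventilator keeps up to 28 ventilator-free days, because the zero rule stops one day before the count does

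*Protocol*

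**What the plan says.** Protocol Section 4.1 makes Day 1 a partial day: "Day 1 is defined as time 0 hours (start of first infusion of study drug) to the end of that calendar day". The 28 full calendar days are therefore Days 2 to 29.

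Section 12.2.6 then states the primary endpoint in these rules:

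- The count: "The number of days after starting unassisted breathing up to and including Day 29", given survival for at least two calendar days after unassisted breathing starts.
- The zero rule: "If a patient was receiving assisted breathing at Day 29 or dies prior to Day 29, VFD will be zero".
- The never-ventilated rule: "If a patient never requires assisted breathing, the VFD will be 28 days".
- The period: "The 28-day study period is from Day 2 to the Day 29+2 telephone contact".

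The 14-day version is to be derived in a similar way. Section 7.6.4 describes VFD as a composite of days off mechanical ventilation and mortality. On survival, Table 1 footnote ad says "28-day survival assessment must take place after a minimum 28 FULL CALENDAR days have elapsed since start of study" and adds an upper limit of two days after Day 29. Footnote f to Figure 1 sets the same minimum.

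**The concern.** Day 29 earns a ventilator-free day, but a death on Day 29 carries no penalty. The zero rule is uneven within one sentence: being on assisted breathing at Day 29 gives zero, while dying that day off the ventilator does not. Because the survival assessment waits until 28 full calendar days have passed, a Day 29 death falls inside the 28-day survival period. The same patient can then be a death for 28-day mortality and a near-best result on the primary endpoint.

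The number of such patients is small, but each is mis-scored by up to the full range of the scale. The 14-day endpoint inherits the same gap at Day 15.

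**Working it through.** **The plan's own figure.** Inputs from Section 13.4: SD 11.380, difference 4.2 VFDs, 100 per arm, one-sided 10%. The standard error is 11.38 × √(2/100) = 1.609, and 4.2/1.609 = 2.610. Power = Φ(2.610 − 1.282) = 0.908, and 97 per arm suffice for 90%. The stated 90% is reproduced.

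**Length of the window.** Day 2 to Day 29 is 29 − 2 + 1 = 28 days. If the period ends at a contact on Day 30 or Day 31, it is 29 or 30 days.

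**Scores under Section 12.2.6 as written.** For a patient last ventilated on Day d who meets the two-day survival condition, VFD = 29 − d. Never ventilated gives 28. Death on Day 28 or earlier gives 0.

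| Last ventilated | Dies Day 28 | Dies Day 29 | Dies Day 30 | Dies Day 29, rule corrected |
|---|---|---|---|---|
| Never | 0 | 28 | 28 | 0 |
| Day 5 | 0 | 24 | 24 | 0 |
| Day 10 | 0 | 19 | 19 | 0 |
| Day 20 | 0 | 9 | 9 | 0 |

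The Day 29 column should match the Day 28 column, but it matches Day 30.

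**How many patients.** The protocol gives no daily hazard, so this part rests on assumptions. Take 28-day mortality m between 23% and 37%, the lowest and highest rates quoted in Section 2.4 (the Phase IIa rates carry no stated day and are treated here as 28-day rates). Let the Day 29 hazard be a fraction f, from 25% to 100%, of the average over the first 28 days:

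- h = f × [−ln(1 − m)]/28, and the share dying on Day 29 is q = (1 − m)(1 − e^(−h)).
- Low end (m = 0.23, f = 0.25): q = 0.18 per 100, or 3 × 0.18 = 0.54 per 300.
- High end (m = 0.37, f = 1): q = 1.03 per 100, or 3 × 1.03 = 3.1 per 300.

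A cruder assumption, a flat daily hazard of 0.2% to 0.5% applied to all 300, gives 0.6 to 1.5 patients.

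**Effect on an arm mean.** The most it can be is 28 × q: 28 × 0.0018 = 0.05 and 28 × 0.0103 = 0.29 VFD. This is a ceiling. It takes every Day 29 death as a patient who would have scored 28, whereas those on assisted breathing that day already score zero.

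**Scale.** One such patient per 100 in one arm and none in the other is 28/100 = 0.28 VFD. Were the true difference to move by that much, power would go from 90.8% to 87.6% or 93.3%.

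**The case against.** The strongest reply is that this is a one-word slip that a statistical analysis plan could settle. It affects very few patients, the same rule applies in every arm, and the sample size is untouched. The points on size stand. The appeal to the analysis plan does not: Section 12.2.6 fixes the derivation rather than deferring it, and a plan that scored Day 29 deaths as zero would depart from the protocol's wording.

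Three stronger readings are tempting, and the documents do not support them.

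- A reader might infer from the telephone-contact sentence that a VFD score depends on when the site calls. It does not. The count, the zero rule and the never-ventilated value are all tied to Day 29 or fixed at 28, and no scoring rule uses the contact date.
- A reader might infer that the Day 29+2 visit window, which nominally opens on Day 29, contradicts footnote ad. But footnotes ad and f restrict that window for survival: the assessment has to follow 28 full calendar days, so it falls after Day 29 has ended.
- Section 7.2.1 says "Whether a patient is alive or not at Day 29+2 and Day 90+14, should be recorded in the eCRF", from which a reader might infer that deaths on Days 91 to 104 enter Day 90 mortality. Nothing says the endpoint is taken from that answer. Section 7.3.3 requires that "All deaths occurring from provision of informed consent until Day 90 must be reported on the statement of death page", and Section 13.3.7 plans a time-to-death analysis, so status at Day 90 can be derived by date.

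**Conclusion.** The point holds as a boundary error in the primary endpoint. As written, a Day 29 death off the ventilator scores as survival, against the composite nature of VFD and the 28-day survival period. The period sentence is loose (28 to 30 days) but harmless to scoring.

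The size is small: roughly half a patient to three patients in 300, and at most about 0.05 to 0.3 VFD in an arm mean. Both ranges rest on the assumed late hazards above. The sample-size calculation reproduces and does not change. This is a minor correction, worth making because the score of an affected patient can swing by up to 28 days on a scale whose assumed SD is 11.38. It does not extend to call-date dependence or to miscounted Day 90 deaths.

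**What to change.** In Section 12.2.6:

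- Extend the zero rule to a death on or before Day 29, and on or before Day 15 for the 14-day version.
- State the study period as Day 2 to Day 29 inclusive, without reference to the telephone contact.
- State that 28-day mortality uses the same cut-off, end of Day 29, applied by date of death.

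The cost is a few sentences in the protocol and the matching line in the derivation program. No visit, sample or patient is added, and the sample size stays as it is.
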